**Effects of intramuscular oxytocin on sensory function in healthy
volunteers with ultraviolet burn injury to the skin**

IRB00056660

NCT03935399

Version Date: 10/17/2019

BACKGROUND

A large body of evidence in animals and in humans suggest that oxytocin can produce analgesia to experimental pain stimuli and relieve pain in acute and chronic clinical pain states. For the past 8 years we have, under an NIH MERIT award, tested the role of the spinal cord in oxytocin's actions by studies in rodents and clinical trials, 3 of which are ongoing, of spinally injected oxytocin.

The Pain Mechanisms Laboratory at Wake Forest is now in the process of assembling an NIH program project grant (P01) on the topic of oxytocin sites, mechanisms, and clinical applications for analgesia, and [name] will lead the clinical project in that proposal. The goal of this IRB protocol is to test whether effects of oxytocin on peripheral nerves observed in physiology experiments in rodents might be applicable to humans and worthy of study more completely in the NIH P01 application in September, 2019.

ANIMAL DATA SUPPORTING THE UNDERLYING PREMISE

Following acute peripheral injury and in many chronic pain states there are changes in sensory response to mechanical stimulation in and surrounding areas of pain. Patients and investigators focus understandably on hypersensitivity, resulting in increased pain to a normally painful stimulus (hyperalgesia) and pain from light touch which is normally not painful (allodynia). Yet, hyposensitivity is as or more prevalent in chronic neuropathic pain, and many chronic pain patients experience both hyper- and hyposensitivity [9; 19; 24]. Gate control theory posits that A β , touch sensitive fiber input acts to reduce A δ and C nociceptor input [18], so loss of A β input could play an important role in the setting of pain.

Over the past 7 years we have recorded from A β and A δ neurons *in vivo*, showing that both are altered after injury and that oxytocin acutely returns their function towards normal [2; 4-6; 23]. Within minutes of peripheral skin incision, during recovery from surgery, and in a model of chronic nerve injury pain, A δ are sensitized, as evidenced by larger receptive fields, lower mechanical threshold in the receptive field for activation, shift in response to a tonic mechanical stimulus from a rapidly adapting, on-

will return twice for testing, first on the day after irradiation and second the following day. At each testing session the area of UV radiation will be heated to 40°C twice separated by 40 minutes.

RANDOMIZED TREATMENT

We propose to take advantage of the stable nature of this model of peripheral injury for 2-3 days in order to apply a randomized, blinded, cross over design with treatment with oxytocin one day and placebo on another. Following baseline measures on each of the two study days, subjects will receive an intramuscular injection of oxytocin (Pitocin®) in its indicated dose of 10 IU (17 µg) or an equivalent volume of saline. In the absence of pregnancy or the postpartum period, doses of oxytocin much greater than this (24-80 IU) produces no physiologic adverse effects when administered intranasally, which produces rapid systemic absorption [15; 17; 21; 27; 32].

RATIONALE FOR PRIMARY OUTCOME MEASURES AND TIMING OF MEASUREMENTS

We will determine thresholds to perception of vibration at a frequency of 256 Hz, pain within the area of UV burn, and area of hypersensitivity to von Frey filament testing before and at the following times after intramuscular study drug injection: 5 minutes, 45 minutes, and 65 minutes. We will also perform a vibration threshold at 30 minutes after the intramuscular injection. These primary outcome measures will assess both A β and A δ /C fiber sensitivity in the area of injury and these times will capture the time of peak plasma oxytocin concentration after intramuscular injection [20].

TEST OF A β FIBER SENSITIVITY

Light touch is subserved by a group of myelinated peripheral nerves with fast conduction in the A β range and which are capable of following high frequencies, being responsible for the sensation of vibration. This capability of individual nerve fibers to respond with high frequency also underlies our ability to sense a light touch moving across the body surface as in brushing.

As noted, preclinical studies show that following injury these light touch fibers become less sensitive to repeated stimulation as occurs with a vibration [2]. Oxytocin,

when perfused around the neuronal cell bodies of these A β nerve fibers, partially restores their function, including their sensitivity to low intensity stimulation.

In order to determine the threshold for perception of vibration, we have created a simple device that produces an oscillatory / vibratory stimulus which can be used on the skin. The subject places the area of interest on the device and the device is set to slowly increase the intensity of vibration at 256Hz until the subject first perceives this. This is repeated twice in the areas of interest. More details on the device are provided in the Appendix.

We anticipate that oxytocin will have no effect on normal A β fibers with testing in normal skin but will decrease the detection threshold for vibration intensity towards normal in the area of UV radiation exposure .

TEST OF A δ FIBER SENSITIVITY

[figure not shown]
Pain threshold to punctate stimulation within the area of irradiation will be determined using calibrated von Frey filaments and an up-down sequential method which efficiently estimates median thresholds [7].

SECONDARY OUTCOME MEASURE: SUSTAINED HEAT

As part of a protocol used by us in several studies, the surface of the skin of the forearm opposite to the area of irradiation is heated to 45°C using an FDA approved, Peltier-controlled thermode for a period of 5 minutes (TSA®, Medoc, Ramat Yishai, Israel). This typically results in a slowly increasing pain experience, peaking at 5 minutes in the mild to low moderate range and has been tolerated by more than 150 subjects in studies over the past 14 years.

In an interim analysis of an ongoing clinical study in volunteers, we noted that spinal injection of oxytocin, 15 µg (equivalent to 9 IU), that pain from this sustained heat was dramatically reduced over the 5 minutes of stimulus presentation (figure). In contrast, spinal oxytocin had no effect on the stimulus-response relationship of pain to noxious heat over a 42-50°C range when the stimuli were presented for only 5 seconds. These data suggest that oxytocin reduces C-fiber mediated signaling of sustained heat pain, likely through a spinal site of action.

Drugs administered spinally have a much higher concentration in cerebrospinal fluid than plasma. Nonetheless, spinally administered drugs are typically absorbed to an extent and with a time course similar to that after intramuscular injection, and it is conceivable that the effect on sustained heat pain we are seeing in the spinal study reflect peripheral effects via systemic absorption. Thus, if we see a similar reduction in response to sustained heat in this protocol of intramuscular administration, we will conclude that oxytocin is more likely activating peripherally than spinally.

Protocol

Effects of intramuscular oxytocin on sensory function in healthy volunteers with ultraviolet burn injury to the skin

PRIMARY GOAL: Provide an estimate of effect size of intramuscular oxytocin on a test of A β and of A δ fiber sensitivity in injured skin following ultraviolet B burned skin.

GENERAL METHODS: Equal numbers of healthy adult men and women will be recruited (ten total) and will have 5 visits in the Clinical Research Unit (CRU) at Wake Forest Baptist Medical Center or Piedmont Plaza 2. In the first visit they will be trained in the experimental procedures to assess pain and perception of vibration and they will receive 3 ultraviolet radiation exposures on the calf of differing intensities surrounding the anticipated minimal erythematous dose (MED). They will return one day later for examination of these sites and determining the MED. At least 5 days later they will return, sensory tests will be repeated and ultraviolet radiation at two times the MED will be exposed to the volar wrist of the dominant hand. The following day and the day thereafter they will return and, after heating the area of the burn to 40°C for 5 min and baseline sensory tests in the area of burn, they will receive an intramuscular injection of either oxytocin (Pitocin®), 10 IU, or saline. The study will be randomized and double blind and all subjects will receive both treatments.

STUDY DESIGN

Inclusion Criteria: We request permission to study up to 12 subjects so that we will have 10 evaluable subjects who have completed all 5 visits.

1. Male or female > 18 and < 60 years of age, Body Mass Index (BMI) <40.
2. Generally in good health as determined by the Principal Investigator based on prior medical history, American Society of Anesthesiologists physical status I
3. Normal blood pressure (systolic 90-140 mmHg; diastolic 50-90 mmHg) resting heart rate 45-100 beats per minute) without medication
4. Female subjects of child-bearing potential and those < 1 year post-menopausal, must be practicing highly effective methods of birth control such as hormonal methods (e.g., combined oral, implantable, injectable, or transdermal contraceptives), double

barrier methods (e.g., condoms, sponge, diaphragm, or vaginal ring plus spermicidal jellies or cream), or total abstinence from heterosexual intercourse for a minimum of 1 full cycle before study drug administration.

Exclusion Criteria:

1. Hypersensitivity, allergy, or significant reaction to any ingredient of Pitocin®
2. Any disease, diagnosis, or condition (medical or surgical) that, in the opinion of the Principal Investigator, would place the subject at increased risk (active gynecologic disease in which increased tone would be detrimental e.g., uterine fibroids with ongoing bleeding), compromise the subject's compliance with study procedures, or compromise the quality of the data
3. Women who are pregnant (positive result for urine pregnancy test at screening visit), women who are currently nursing or lactating, women that have been pregnant within 2 years.
4. Subjects with neuropathy, chronic pain, diabetes mellitus, or taking benzodiazepines or pain medications on a daily basis.

Study Visit 1: The participant will report to the CRU or Piedmont Plaza 2. The participant will review and sign the Informed Consent. After informed consent is adequately obtained, a detailed medical history will be obtained from the participant, female participants will provide a urine sample to determine pregnancy status. The research nurse will train the participants to estimate pain quantitatively using a 2 cm² Peltier controlled thermode (TSA®) applied to a forearm with 5 sec presentation of stimuli at 39, 41, 43, 45, 47, 49, and 50°C, using a 11 point numerical verbal scale (NRS) anchored at 0 for no pain and 10 for the worst pain imaginable . Typically, the participant is exposed to temperatures between 38° and 51° C using a random staircase method. After this training, we will ask them to report pain intensity on the 0-10 NRS scale every minute for 5 minutes upon exposure to a 4 cm² Peltier controlled thermode at 45°C to the lateral calf. Finally, the subject will place the palmar aspect of the wrist of their dominant hand on a device and report when they first perceive a sensation as the intensity of vibration at a fixed frequency of 256 Hz is slowly increased. We have found

this training session significantly reduces anxiety and variability in pain and hypersensitivity ratings on subsequent study days.

Ultraviolet-B light exposure will be controlled by a commercially available solar simulator and dose control system that meets specifications for FDA sunscreen testing (Solar Light Co., Inc). The solar simulator consists of a 150-watt xenon bulb that produces the full range of solar ultraviolet energy (290-400 nm) without exposing subjects to thermal energy. Exposure is limited to a 3 cm² diameter circle of skin and, after an individualized determination of dose, produces moderate erythema that is sensitive to thermal and mechanical stimulation. During this visit three areas of skin on the subject's calf will be exposed to ultraviolet light for different lengths of time not to exceed 200 seconds. This procedure is not painful, and this burn does not produce spontaneous pain as the burn injury resolves over the next several days.

Study Visit 2

The subject will return to the CRU or Piedmont Plaza 2 24 hours later and the exposed areas evaluated for UV-induced erythema. The purpose of this procedure is to determine each subject's MED, defined as the dose of UV light that produces clear redness with sharply demarcated borders.

Study Visit 3

The subject will report to the CRU or Piedmont Plaza 2 at least 5 days after study visit 2. After determination of vibration frequency perception threshold on the dominant arm volar aspect of the wrist, the center of the volar aspect of the wrist will be irradiated with an ultraviolet exposure of 2 times the subject's MED. Subjects will be instructed that they can take acetaminophen as needed, but not NSAIDs, over the next 2 days, but that they should not take acetaminophen within 6 hours of study visits 4 and 5.

Study Visit 4

The subject will report to the CRU the day after Study Visit 3. Baseline blood pressure, heart rate and respiratory rate will be measured. Baseline measures will be obtained to include 5 minute presentation of a 45°C stimulus to the lateral calf, perception threshold of vibration intensity on the dominant arm site of ultraviolet burn, and pain threshold using application of calibrated von Frey filaments to the site of ultraviolet burn. Finally, we will map the area of hypersensitivity surrounding the burn

site using a 225mN von Frey filament. Following baseline measurements we will apply the Peltier controlled thermode to the burn site and increase the probe temperature to 40°C for 5 min. Immediately after removing the probe the subject will receive an intramuscular injection of oxytocin (Pitocin®), 10 IU or the same volume (1 ml) of saline. Thresholds to perception of vibration and pain within the area of UV burn and areas of hypersensitivity surrounding the burn area will be determined 5 minutes, 45 minutes, and 65 minutes after injection. A vibratory threshold will also be determined at 30 minutes after the injection. Pain report to a 5 minute presentation of the 45°C stimulus to the lateral calf will be determined at the 20 and 60 min time period after injection. The area of the burn site will be heated to 40°C for 5 min a second time, 40 min after the first.

Study Visit 5

All procedures from Study Visit 4 will be repeated with the cross-over study drug solution.

Safety and Monitoring: Given that oxytocin is available over the counter in much larger systemic doses than proposed in this application and since multiple scientific reports have examined much larger systemic doses than in this application using only subjective reporting, we propose to only request subjects to report any unusual sensations and query them at the end of each drug administration study day if they experienced any unusual sensations. UV protective glasses will be worn by study staff administering the UV exposure. The subject will be shielded with a barrier so there will be no exposure to their eyes.

Blood pressure, heart rate and respiratory rate will be measured on study visits 4 and 5 at baseline and then at 30 and 60 minutes after the injection.

RISKS

Risks of intramuscular injection include pain and bruising. Risks from the FDA approved heat stimulus device are pain, and the subject can stop testing at any time if the pain they perceive is such that they do not want to continue. Please note that these devices are used in many pain clinics routinely and have multiple fail-safe designs to

avoid thermal burn. Risks from the non-regulatory vibratory device are related only to microshock and are addressed in the Appendix. Risks from the Electromechanical Risks from the UV radiation causes mild sunburn, and may blister or hurt for a few days. The sunburned skin will almost always tan in normal individuals, and may tan more darkly than the surrounding skin for several weeks to several months. It is possible that the darker patches of skin may be present for up to a year. Long-term darkening (discoloration) or scarring is possible, but rare in people with normal skin and a history of normal tanning. Repeated exposure of the skin to UV light is known to produce photoaging (aging of the skin in response to sunlight) and carries the risk of photo carcinogenesis (skin cancer). However, the few exposures in this study, equivalent perhaps to one hour of casual sun exposure during the summer, produces an insignificant increase in lifetime risk.

Risks of oxytocin are primarily restricted to uterine contraction in the presence of pregnancy, since oxytocin receptors are not present in the non-pregnant uterus (Package insert attached). Additionally there is the possibility of a feeling of being flushed, headache and increased heart rate with no significant change in blood pressure during or immediately after the infusion. These events have been reported by previous participants but were short lived, lasting approximately 12-15 minutes.

Data Safety Monitoring Plan

Although the use of oxytocin in this protocol is outside FDA approval for oxytocin administration during the postpartum period, the dose to be studied is similar to or less than that of multiple recent studies in healthy volunteers with intranasal oxytocin purchased over the counter in the US [10; 12-15; 17; 20-22; 25-32] and without description of adverse events. For these reasons, we do not propose a data safety monitoring committee or special safety evaluation beyond those required by IRB regulations.

Minority, Gender, and Children Participation

Both sexes and races and ethnicities will be actively recruited in this small study. Children under age 18 are not included in these protocols because this protocol because the safety of this product has not been established in children.

Volunteer Payment

Participants will be paid a total of \$500 according to the following payment schedule which we have used throughout the last 2 cycles of this grant's protocols. We believe that this payment schedule is fair and appropriate, paying for each procedure attempted and an additional payment for completion of the entire study.

Completion of study visit 1: \$50

Completion of study visit 2: \$25

Completion of study visit 3: \$25

Completion of study visit 4: \$50

Completion of study visit 5: \$350

Long-term Follow-up

Volunteers will be contacted daily within the following week after the last study visit and questioned about adverse events from the study.

STATISTICAL RATIONALE

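### Does the forearm-versus-calf conflict over the sustained-heat site undermine the planned comparison with the spinal oxytocin study?

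*Combined protocol and SAP*

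**What the plan says.** The section SECONDARY OUTCOME MEASURE: SUSTAINED HEAT introduces the test as a method the group has used in several studies and states that "the surface of the skin of the forearm opposite to the area of irradiation is heated to 45°C" for five minutes. It then reports, from an interim analysis of an ongoing volunteer study of spinal oxytocin, that "pain from this sustained heat was dramatically reduced over the 5 minutes of stimulus presentation". The Background confirms that the group itself runs such studies, referring to "clinical trials, 3 of which are ongoing, of spinally injected oxytocin".

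The section closes with an inference: "if we see a similar reduction in response to sustained heat in this protocol of intramuscular administration", then "we will conclude that oxytocin is more likely activating peripherally than spinally".

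The visit procedures name a different site. At Study Visit 1 subjects rate pain "upon exposure to a 4 cm² Peltier controlled thermode at 45°C to the lateral calf". At Study Visit 4 the baseline includes a "5 minute presentation of a 45°C stimulus to the lateral calf", and after injection "Pain report to a 5 minute presentation of the 45°C stimulus to the lateral calf will be determined at the 20 and 60 min". Study Visit 5 repeats Visit 4 with the other study drug. The Statistical Rationale does not list sustained heat among the co-primary outcomes and plans descriptive statistics as the primary analysis of this pilot.

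**The concern.** One test has two stated sites, and nothing in the text reconciles them. The forearm sentence can be read in three ways:

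- **A.** It describes this trial and contradicts the visit procedures.
- **B.** It describes the group's earlier method. The spinal result would then be a forearm result set against a calf result here.
- **C.** Forearm is a slip, and both studies used the calf.

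Reading B is the one that would matter. Arm and leg input enters the spinal cord at different levels. If the spinal injection was lumbar (an assumption; the level is not given), the spinal drug might act unequally on the two limbs, whereas a systemic drug need not. Two reductions of similar size at different sites would then be a weaker guide to where the drug acts. The site-of-action statement is also the only conclusion that the protocol commits to in advance, so its comparator ought to be clear.

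**Working it through.** No sample size, power or error rate is involved, so the check is mainly a comparison of the texts.

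**1. Where the five-minute 45°C test is placed**

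| Place in the protocol | Site | Presentations |
|---|---|---|
| SECONDARY OUTCOME MEASURE: SUSTAINED HEAT (rationale) | forearm | none scheduled |
| Study Visit 1 (training) | lateral calf | 1 |
| Study Visit 4: baseline, 20 and 60 min | lateral calf | 3 |
| Study Visit 5 (repeats Visit 4) | lateral calf | 3 |

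Outcome presentations per subject: 3 × 2 = 6. In 10 evaluable subjects: 6 × 10 = 60. None is on the forearm. In the visit procedures, forearm heat outside the burn site appears only as the 5-second training stimuli at Visit 1. The conflict is therefore real, but it lies between one rationale sentence and a schedule that agrees with itself.

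**2. Effect on this trial's own estimate.** Each subject is tested at the same stated site under oxytocin and under saline. The contrast between the two is unaffected by what the rationale calls that site.

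**3. Does accepting the calf create another problem?** The calf also receives the three UV exposures at Visit 1. Earliest days are: Visit 1 on day 0, Visit 2 on day 0 + 1 = 1, Visit 3 on day 1 + 5 = 6, Visit 4 on day 6 + 1 = 7. The longest stated duration of skin sensitivity is 3 days, so the first outcome test comes at least 7 − 3 = 4 days after it has passed.

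**4. Is a site mismatch between the studies shown?** Three points bear on this.

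- The forearm sentence stands under this trial's own outcome heading.
- It locates the test relative to irradiated skin. This trial irradiates a wrist, and no irradiation is mentioned for the spinal study.
- The spinal result is tied to that sentence only by a back-reference, which can equally mean the same stimulus (45°C for 5 minutes). The figure cited for that result is not reproduced in the text available here, so it can neither confirm nor exclude a site.

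Reading A is the most direct of the three. Reading B is possible but is an inference.

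**5. What if reading B were true?** The doses are close: 17 µg intramuscular against 15 µg spinal, a ratio of 17/15 = 1.13. The section raises the possibility that the spinal result reflects systemic absorption. A fall in calf heat pain after intramuscular oxytocin, relative to saline, would show that systemic exposure at about that dose can produce the effect. That supports the stated conclusion whatever site the spinal study used. A site difference would weaken the comparison of the sizes of the two reductions, but would not empty it.

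**6. Would matched sites make the inference firm?** No. The protocol sets no numerical criterion for a similar reduction, the comparator is a separate study, and the planned analysis is descriptive. The inference is interpretive with or without matched sites.

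**The case for a change.** The best case for a change is that the inference needs comparable tests, and that the only text bearing on the spinal study's heat site says forearm. Site is not a neutral detail when the question is spinal against peripheral action. The trial schedules no five-minute forearm test, so its data cannot estimate or adjust for a forearm–calf difference. The remedy is cheap, because the group can look up its own spinal study and soften the conclusion if the sites differ.

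Part of this stands. The two descriptions conflict and must be reconciled in wording, and whoever reports the comparison should state the heat site in each study and say so if they are not matched. That is ordinary reporting, and the group holds the information.

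The rest does not carry. Softening the conclusion depends on a mismatch that the documents do not show. The claim that a site difference would make the result unreadable goes too far, because a systemic drug need not act differently on arm and leg and the conclusion is stated only as more likely. The count of 0 in 60 restates the wording conflict and does not measure bias.

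**Conclusion.** No change to the plan is needed. The forearm wording is a clerical inconsistency in rationale text, and the missing site of the spinal study's test is a detail that the authors can supply when they interpret the result. Correcting either would change none of the 60 scheduled outcome presentations, the oxytocin–saline contrast or the three co-primary outcomes. At most, a true site difference would call for a caveat on comparing the size of the reduction across studies, for a secondary outcome in a descriptive pilot.

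This rests on two assumptions: that staff follow the visit procedures, so that the calf is the site actually tested, and that the eventual report names the sites. How much forearm and calf differ in sustained-heat pain, or in response to spinal oxytocin, cannot be derived from the documents.

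### A fall in sustained-heat pain after intramuscular oxytocin would show that systemic exposure is sufficient, not that the site of action is peripheral

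*Combined protocol and SAP*

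**What the plan says.** The argument is in the protocol section Secondary Outcome Measure: Sustained Heat. It starts from a result found "In an interim analysis of an ongoing clinical study in volunteers": 15 µg of spinal oxytocin markedly lowered pain from five minutes of heat at 45°C but did not change pain from five-second stimuli. The section first reads this as reduced C-fibre signalling, "likely through a spinal site of action".

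It then raises one alternative. It notes that "Drugs administered spinally have a much higher concentration in cerebrospinal fluid than plasma", but adds that spinal drugs are usually absorbed about as much, and about as fast, as intramuscular ones. From this it says that "it is conceivable that the effect on sustained heat pain we are seeing in the spinal study reflect peripheral effects via systemic absorption".

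The consequence is fixed in advance. If this trial sees a similar reduction, "we will conclude that oxytocin is more likely activating peripherally than spinally".

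The Randomized Treatment section gives oxytocin "in its indicated dose of 10 IU", stated there to be 17 µg, or an equal volume of saline. Study Visit 4 schedules the sustained-heat test at baseline and at 20 and 60 min after injection. The Statistical Rationale names three co-primary measures, proposes descriptive statistics, and gives no analysis for sustained heat.

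**The concern.** The alternative to a spinal site is introduced as a peripheral effect arising from systemic absorption. From there on, systemic and peripheral are treated as the same thing. They are not: an intramuscular dose exposes every site that circulating drug can reach, and peripheral tissue is only one of these. The body of the protocol does not mention a supraspinal site.

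The trigger for the conclusion also cannot be applied as written. No size, margin or interval defines a similar reduction, and this trial has no spinal arm. The judgement would therefore rest on an informal comparison with an interim result from another study.

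What is at stake is the label on the finding. The Background says that the grant application concerns where and how oxytocin acts. Followed as written, the plan would report as peripheral a result that shows only that systemic exposure is enough.

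**Working it through.** **Inputs from the documents.** Spinal dose 15 µg, stated as 9 IU (Sustained Heat). Intramuscular dose 10 IU, stated as 17 µg (Randomized Treatment). Treatments: intramuscular oxytocin and saline, each subject receiving both (General Methods). Evaluable subjects: 10, from up to 12 (Study Design). No SD, margin or expected effect is given, so precision is stated in units of the SD of the within-subject differences.

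**Step 1: are the two doses comparable?** The plan's own conversion gives 15 × 10/17 = 8.82 IU, which rounds to its stated 9 IU. The intramuscular-to-spinal ratio is 17/15 = 1.13 in µg, or 10/9 = 1.11 in IU. The doses are close, so the plan's exposure argument can be granted.

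**Step 2: what does each candidate site predict?** Take the plan's premises as true: similar systemic exposure by both routes, and a much higher cerebrospinal fluid (CSF) level after spinal dosing.

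| Site of action | Would intramuscular dosing be expected to give a similar fall? |
|---|---|
| Spinal, driven by the high CSF level | No, if little drug reaches the CSF from the circulation and the spinal dose was not far above what the full effect needs |
| Spinal, reached from the circulation | Possible |
| Peripheral | Yes |
| Supraspinal, reached from the circulation | Yes |

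A similar fall therefore lowers the standing of the first row relative to the third, which is the comparison the plan makes. It does not separate the third row from the fourth, and it does not exclude the second. Separating them would need another route of administration or a measure of exposure at the candidate sites. The visit schedule contains neither.

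**Step 3: how precisely will the trial estimate its own contrast?** For a simple paired 95% interval, ignoring any period effect, the half-width is t(0.975, n−1)/√n.

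- n = 10: 2.262/3.162 = 0.72 SD
- n = 12, if all were evaluable: 2.201/3.464 = 0.64 SD

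**Step 4: how precise would a comparison with the spinal study be?** Its size and SD are not given. As an assumption only, let it supply m within-subject differences with the same SD. The half-width is t(0.975, 10+m−2) × √(1/10 + 1/m).

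- m = 10: 2.101 × 0.447 = 0.94 SD
- m = 40: 2.011 × 0.354 = 0.71 SD

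On these assumptions, without a criterion, quite different intramuscular effects could be described as similar.

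**Step 5: is the stimulus the same throughout?** The Sustained Heat section places it on "the surface of the skin of the forearm opposite to the area of irradiation". Study Visits 1 and 4 place it on the lateral calf. If the first passage describes this trial, the protocol contradicts itself. If it describes the earlier studies, the comparison with the spinal result may cross body sites. Either way the passages must be reconciled before the two studies are compared.

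**The case against.** The strongest reply is that the sentence is a hedged comparison in background text. A reader might infer that the plan ranks peripheral action above supraspinal action. It does not: the sentence compares peripheral only with spinal, and on the plan's own premises that comparison is reasonable. Nor does the plan claim to exclude a spinal site. This stands, and it limits the point to an omitted alternative and a label that says too much.

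The documents also give little support to a supraspinal site. Two cited titles bear on it: an intranasal study reporting changed amygdala activity, and a macaque study reporting that intranasal and intravenous oxytocin reach the CSF. Neither used the intramuscular route, and titles alone cannot show how plausible the site is here. The plan also has evidence on mechanism in the contrast between sustained and five-second heat. That contrast bears on the type of fibre signal, however, and does not separate a peripheral from a supraspinal site. The point needs only that the design leaves the alternative open.

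A further reply is that asking for a similarity criterion in a descriptive pilot is mere preference. Taken alone, the undefined word would indeed be only missing detail, and the comparator's figure is not visible in the text available here. It matters because a site-of-action conclusion is tied to it.

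A reader might also infer that pain ratings at the treatment visits are unspecified. That goes too far. Study Visit 1 trains subjects on the same calf stimulus, where they "report pain intensity on the 0-10 NRS scale every minute for 5 minutes", and the natural reading carries this forward.

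**Conclusion.** The concern holds as a minor point. A fall in sustained-heat pain after intramuscular oxytocin would show that systemic exposure is sufficient. If comparable with the spinal result, it would also make a purely spinal site less likely, given the plan's premises on dose, absorption and CSF level. It would not locate the effect in the periphery.

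The consequence is small. This is a secondary outcome in a descriptive pilot, and the co-primary outcomes are untouched. The follow-on study in the Statistical Rationale, which would relate effect to plasma concentration under intravenous infusion, needs only the systemic reading.

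The conclusion about site rests on the design alone and does not depend on any assumed effect size. The 0.72 SD half-width rests on 10 evaluable subjects and a simple paired interval; the between-study half-widths are illustrative.

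**What to change.** Replace the sentence that fixes the conclusion with wording such as:

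> The oxytocin-minus-saline difference in sustained-heat pain at 20 and at 60 min will be reported with 95% CIs. A reduction will be interpreted as showing that systemic exposure is sufficient for the effect; it would make a purely spinal site less likely but would not distinguish peripheral from supraspinal action, or exclude a spinal site reached from the circulation. Any comparison with the spinal study will be descriptive, without a claim of similarity.

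Also reconcile the heat-stimulus site between the Sustained Heat section (forearm) and Study Visits 1 and 4 (lateral calf) before any such comparison.

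The change is to wording only. It adds no subjects, visits or procedures. The price is a weaker mechanistic claim, which the planned follow-on study does not depend on.
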